Introduce eDiary including assess patient capability to use eDiary	X				
Provide study eDiary and provide detailed instructions and complete EQ-5D-5L		X			

Procedure	Visit 1 ^a Screening	Visit 2 Baseline	Treatment period ^b Treat moderate/severe migraine attack within 4 hrs of pain onset	Visit 3 EoS or EDC ^c	Note
		+7~30 days after V1	8 weeks	3~28 days after treatment OR At 8 weeks after V2 ^d	
Migraine attack (eDiary) documentation by patient			X		Patients will enter data into the eDiary at 0 (pre-dose), 0.5, 1, 1.5, 2, 3, 4 and 24 and 48 hours after dosing. Details are described in Appendix 5 . In addition to entering data during migraine attacks, patients will be reminded daily to record any adverse events and any new concomitant medication(s) during the treatment period.
Provide study paper diary and detailed instructions		X			
Documentation of adverse events and concomitant medication (paper diary)			X		
Documentation of non-study rescue/recurrence medication (paper diary)			X		
Document menstrual cycle status (paper diary)			X		
Assessment of driving accidents/violations		X		X	
Determine compliance study drug				X	
Collect unused/empty study drug pack, eDiary, and paper diary				X	

Abbreviations: C-SSRS = Columbia Suicide Severity Rating Scale; CVD = cardiovascular disease; DNA = deoxyribonucleic acid; ECG = electrocardiogram; EDC = early discontinuation; eDiary = electronic diary; EoS = end of study; EQ-5D-5L = EuroQol 5 Dimension 5 Level; FHS = follicle stimulating hormone; ICHD-2 = International Classification of Headache Disorders 2nd Edition; IHS = International Headache Society; MIDAS = Migraine Disability Assessment Test; mTOQ6 = Migraine Treatment Optimization Questionnaire; SHSF = self-harm supplement form; SHFU = self-harm follow-up form; V = visit; WOCBP = women of child-bearing potential.

- ^a V1 activities to be collected outside migraine attack.
- ^b During the treatment period, unscheduled visits may be completed at the discretion of the investigator.
- ^c Patients who do not treat a migraine with study drug for any reason during the study should attend an EoS visit to return unused study drug and the eDiary. Adverse events and use of concomitant medications must be assessed, however no other assessments are required.
- ^d Patients who do not treat a migraine with study drug should attend this visit at 8 weeks after V2. Visit 3 should be finished by 8 weeks (+14 days as visit allowance) after V2.

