10.1.1. Sample Size Rationale

Table LAIH.5 illustrates the power calculation.

The power calculation is based on the results of the Study 302/LAHK study. The primary endpoint (headache pain free at 2 hours postdose) results in Study 302/LAHK were 21.3%, 28.6%, 31.4%, and 38.8% for placebo, lasmiditan 50 mg, lasmiditan 100 mg, and lasmiditan 200 mg, respectively, and the rates of headache pain relief at 2 hours postdose were 47.7%, 59.0%, 64.8%, and 65.0% for placebo, lasmiditan 50 mg, lasmiditan 100 mg, and lasmiditan 200 mg, respectively.

To ensure sufficient total statistical power for the primary and two key secondary analyses, the number of randomized patients will be set at 880. This sample size has 85.6% power. More specifically, the study will include:

- Number of screened patients = 1157.
- Number of randomized patients = 880 (= 1157*0.76, approximately 24% screen failure based on assumptions from LAIJ), with [placebo:lasmiditan 50 mg:lasmiditan 100 mg:lasmiditan 200 mg] = 268:114:268:230 (7:3:7:6 ratio) for the attack.
- Number of patients who have an attack = 624 (= 880*0.71, approximately 29% of patients would not dose to treat a migraine attack during the 8 week period based on Study 302/LAHK/Study 301/LAHJ), with [placebo:lasmiditan 50 mg:lasmiditan 100 mg:lasmiditan 200 mg] = 190:81:190:163 (7:3:7:6 ratio).

Table LAIH.5. Study Power Calculation

	Arm	N
Arm and number of patients	PLA	190
	LY50	81
	LY100	190
	LY200	163
	Total	624
Power	Primary [T1] : PLA vs LY200 = 93.6% (2 sided, alpha = 0.05) Key secondary [T2]: CA (PLA,LY50,LY100,LY200) = 94.9% (2 sided, alpha = 0.05)	

	Key secondary [T3]: PLA vs LY100 = 91.2% (2 sided, alpha = 0.05) Total (primary and two key secondaries) = 85.6%
Primary endpoint/Key secondary endpoints	[T1] and [T2]: Pain free at 2 hours postdose [T3]: Pain relief at 2 hours postdose

Abbreviations: alpha = type 1 error; CA = Cochran Armitage trend test; LY200 = lasmiditan 200 mg; LY100 = lasmiditan 100 mg; LY50 = lasmiditan 50 mg; PLA = placebo; N = number of patients for the corresponding arms which correspond to modified ITT (mITT) population.

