- For Kaplan-Meier analysis, corresponding figures will be created. Quartiles and rates, along with 95% CIs, were estimated using the Kaplan-Meier method. Corresponding 95% CIs were estimated using the methods of Brookmeyer and Crowley, and Greenwood, respectively.
- When baseline usage of preventive medications to reduce the frequency of migraine (Yes/No) is included in a statistical model, it is based on CRF, not IWRs.
- Efficacy analyses are based on eDiary data, unless otherwise specified.
- Comorbid condition is based on Visit 1.
- When median is used for subgroup analysis (e.g. SUB4, body weight), the median is based on mITT population.

We will use the following analysis population rules unless otherwise specified (see population definitions in Section [5.3](#)):

- Protocol deviation summary will be based on all randomized and mITT/ITT.
- Demographics and Baseline characteristics will be based on mITT/ITT/safety population (SP).
- Efficacy analyses [T1], [T2], [T3], and MBS will be based on mITT/ITT/per-protocol set (PPS).
- Other efficacy and health outcome will be based on ITT.
- Safety analyses (e.g., AE, laboratory assessments/vital signs), medication, and treatment compliance/eDiary compliance will be based on SP.

When continuous variables, including change from baseline scores, is summarized using descriptive statistics, it will show n (number of subjects with available data), mean, median, standard deviation, minimum, and maximum.

Minimum and maximum values will be presented to the same precision as the raw data. Mean and median will be presented to one more decimal place than the raw data. Standard deviation will be presented to two more decimal places than the raw data. P-values will be presented to three decimal places.

Categorical variables will be summarized using counts and percentages. Unless otherwise specified, percentages will be calculated using the numbers of subjects in the summarized

population in each treatment group as denominators. Percentages will be presented with a precision of 1 digit after the decimal.

Observations collected prior to dosing will serve to determine a baseline measurement; the latest available measurement prior to dosing will be used as the baseline. For data collected by eDiary, the baseline values will be the Hour-0 assessment times identified in the eDiary.

SAS® software (version 9.2 or higher) will be used to perform most or all statistical analyses.

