- Post-dose AEs
 - By PT by decreasing frequency
 - By SOC/PT (sorted alphabetically by system organ class (SOC), then by frequency in preferred term (PT))
- TEAEs by PT considered to be related to investigational product by investigator
- TESAEs by PT
- TESAEs by PT considered to be related to investigational product by investigator
- SAEs by PT

Listing of AE (with TEAE flag) will be created for all randomized population

List of SAE will be created.

Note: If multiple severities are reported for a given AE and subject, then the most severe intensity will be counted. The same rule is applied for TEAEs.

Note: Patients were told not to report symptoms that usually occurred during migraine attacks (e.g. nausea).

Note: For events that are gender-specific, the denominator and computation of the percentage will include only patients from the specific gender.

5.7.2. *Columbia-Suicide Severity Rating Scale (C-SSRS)*

The C-SSRS will be used to assess suicidal ideation, suicidal behavior, and self-injurious behavior without suicidal intent. At Visit 1, the screening version will be used to assess suicidal ideation and behavior during the lifetime and in the past one month. At the following visits (Visit 2, EOS/Visit 3), the Since Last Visit version will be used to assess suicidal ideation and behavior since the last visit.

The following outcomes are C-SSRS categories and have binary responses (yes/no).

Category 1 – Wish to be Dead

Category 2 – Non-specific Active Suicidal Thoughts

Category 3 – Active Suicidal Ideation with Any Methods (Not Plan) without Intent to Act

Category 4 – Active Suicidal Ideation with Some Intent to Act, without Specific Plan

Category 5 – Active Suicidal Ideation with Specific Plan and Intent

Category 6 – Preparatory Acts or Behavior

Category 7 – Aborted Attempt

Category 8 – Interrupted Attempt

Category 9 – Actual Attempt (non-fatal)

Category 10 – Completed Suicide

Self-injurious behavior without suicidal intent is also a C-SSRS outcome (although not suicide-related) and has a binary response (yes/no).

Composite endpoints based on the above categories are defined below.

- Suicidal ideation: A “yes” answer at any time during treatment to any one of the five suicidal ideation questions (Categories 1-5) on the C-SSRS.
- Suicidal behavior: A “yes” answer at any time during treatment to any one of the five suicidal behavior questions (Categories 6-10) on the C-SSRS.

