- Suicidal ideation or behavior: A “yes” answer at any time during treatment to any one of the ten suicidal ideation and behavior questions (Categories 1-10) on the C-SSRS.

Summary of 10 categories and “Self-injurious behavior without suicidal intent” will be created for baseline (Visit 1 and Visit 2 separately) for safety population and for all randomized population.

Summary of 10 categories and “Self-injurious behavior without suicidal intent”, and 3 composite endpoints will be summarized will be created for post baseline for safety population and for all randomized population.

Listings will present all C-SSRS data for subjects with at least one positive response to any C-SSRS question at any time during the study for all randomized population

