5.7.6. Assessment of Driving Incidents

Assessment of accidents/violations will be listed by patient (all randomized population). Summary table will be created (baseline and postbaseline)

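### The all-randomized post-baseline C-SSRS table divides by patients for whom no post-baseline C-SSRS is required, so its percentages can fall to about 0.71 of the rate among those assessed (minor)

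*SAP*

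**What the plan says.** **Population.** SAP 5.7.2 plans a post-baseline summary of the ten C-SSRS categories, self-injury without suicidal intent and three composites. It "will be created for post baseline for safety population and for all randomized population". The section gives no denominator.

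**Denominator.** The general rules in SAP 5.4 therefore apply. "Categorical variables will be summarized using counts and percentages", and, unless another rule is stated, "percentages will be calculated using the numbers of subjects in the summarized" "population in each treatment group as denominators" (one sentence, running over a line break).

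**Timing.** SAP 5.7.2 treats Visits 1 and 2 as baseline. The Schedule of Activities and Protocol 9.4.4 place the C-SSRS at Visits 1, 2 and 3 only. At Visits 2 and 3, "the Since Last Visit version will be used to assess suicidal ideation and behavior since the last visit". Visit 3 is thus the only scheduled post-baseline C-SSRS.

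**Who needs it.** For patients who do not treat an attack with study drug, footnote c of Table LAIH.2 says of the end-of-study visit: "Adverse events and use of concomitant medications must be assessed, however no other assessments are required". Protocol 5.2 repeats the rule.

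**How many.** Protocol 10.1.1 expects that "approximately 29% of patients would not dose to treat a migraine attack during the 8 week period".

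**Contrast.** For hepatic laboratory elevations, SAP 5.7.4 limits the percentages to patients who have a post-baseline value. SAP 5.7.2 has no such rule.

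**The concern.** A patient with no Visit 3 C-SSRS cannot contribute a positive answer but is still counted below the line. The percentage then behaves as if that patient had answered no to every question. SAP 5.4.1 leaves the value missing and does not impute it, but it does not take the patient out of the denominator either.

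What is at stake is the absolute rate of suicidal ideation and behavior in one of the two planned tables. A reader of the all-randomized table would see a lower rate than was found among the patients who were asked, with nothing on the page to show how many were not asked.

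**Working it through.** **Inputs** (Protocol 10.1.1; same figures in SAP 5.2)
- Randomized: 880, as placebo 268, 50 mg 114, 100 mg 268, 200 mg 230.
- Treating an attack: 624, as 190, 81, 190, 163.
- Assumption for the base case: every dosed patient has a Visit 3 C-SSRS and no undosed patient has one.

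**Step 1. Reproduce the plan's figure.** 880 × 0.71 = 624.8, against 624 stated. The plan's numbers hold.

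**Step 2. Patients with no required post-baseline C-SSRS** (randomized − dosed)

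| Arm | Randomized | Dosed | Undosed | Undosed share | Dosed / randomized |
|---|---|---|---|---|---|
| Placebo | 268 | 190 | 78 | 29.1% | 0.709 |
| 50 mg | 114 | 81 | 33 | 28.9% | 0.711 |
| 100 mg | 268 | 190 | 78 | 29.1% | 0.709 |
| 200 mg | 230 | 163 | 67 | 29.1% | 0.709 |
| Total | 880 | 624 | 256 | 29.1% | 0.709 |

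**Step 3. Dilution factor.** With x positive patients, the table shows x / randomized, and the rate among those assessed is x / assessed. The ratio of the two is assessed / randomized = 624 / 880 = 0.71. With the assessed as denominator, each percentage rises by 880 / 624 = 1.41.

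**Step 4. Range if some undosed patients are assessed anyway.** With a share f of the 256 assessed, the factor is (624 + 256f) / 880.
- f = 0.25: 688 / 880 = 0.78
- f = 0.50: 752 / 880 = 0.85
- f = 1: 880 / 880 = 1.00

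**Step 5. Range in the undosed share** (assumed values, none of the undosed assessed). At 20% undosed the factor is 0.80; at 35% it is 0.65.

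**Step 6. Illustration** (event counts are assumed, not taken from the documents)
- 5 positive patients overall: 5 / 880 = 0.57% against 5 / 624 = 0.80%.
- 2 in placebo: 2 / 268 = 0.75% against 2 / 190 = 1.05%.
- 2 in the 50 mg arm: 2 / 114 = 1.75% against 2 / 81 = 2.47%.

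**The case against.** **Arguments for leaving the plan alone, and what stands**

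- *The correct denominator is already on view.* The safety population is dosed patients only (SAP 5.3), so its table contains none of the undosed. SAP 5.7.2 also lists all C-SSRS data for every randomized patient with any positive answer, so no recorded case is hidden. This stands and confines the problem to one table.
- *No comparison is distorted.* Safety output is descriptive with no test (SAP 5.4), and the planned undosed share is about 29% in every arm, so ratios between arms barely move. This stands under the planning assumption.
- *Footnote c removes a requirement; it forbids nothing.* Undosed patients have the C-SSRS at Visits 1 and 2, and a site may do it at Visit 3. For patients who discontinue before dosing, Protocol 8.1 also points to Section 9.4, which contains the C-SSRS. It points equally to Section 2, where footnote c is attached to the end-of-study and early-discontinuation column and covers any reason for not dosing. The text is ambiguous, which is why 0.71 must be given with a range.
- *Missing stays missing.* This is true of the value under SAP 5.4.1. It does not change the denominator set in SAP 5.4, so it does not answer the point.

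**Stronger readings that a reader might infer**

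- *The Visit 3 look-back mislabels pre-dose events as occurring during treatment.* The documents do not support this. Protocol 5.1.2 starts the treatment period at Visit 2, so a look-back to Visit 2 fits that label. The table is described as post-baseline and does not claim to be post-dose.
- *Driving incidents have the same fault.* SAP 5.7.6 says "Assessment of accidents/violations will be listed by patient (all randomized population", but that item is a listing, and a listing has no denominator. No population is named for the driving summary table, and the SAP 5.4 default for safety analyses is the safety population. No error is shown.
- *Neither C-SSRS table can be used.* This fails because the safety-population table contains no undosed patients.

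**Conclusion.** The point holds, and it is minor. Followed as written, SAP 5.7.2 together with SAP 5.4 produces an all-randomized post-baseline C-SSRS table whose percentages understate the rate among assessed patients by up to about 29% in relative terms.

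That size rests on three assumptions: the planned 29% who never dose, no Visit 3 C-SSRS in any of them, and a Visit 3 C-SSRS in every dosed patient. Under the planned 29%, 0.71 is the low end, and the factor approaches 1.00 as more of the undosed are assessed. Counts and listings are unaffected. The consequence is an understated absolute rate in one descriptive table, not a biased treatment comparison.

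**What to change.** In SAP 5.7.2, state that percentages in the post-baseline summaries use patients with at least one post-baseline C-SSRS as the denominator, and that each table shows the number assessed and not assessed per arm. This follows the post-baseline-value rule that SAP 5.7.4 already applies to hepatic tests.

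The cost is one line of SAP text and a small change to the table shell. No data collection changes: no field for timing relative to the dose is needed, and SAP 5.7.6 can stay as it is. One consequence to expect is that, if no undosed patient is assessed, the all-randomized table will cover nearly the same patients as the safety-population table. What it would then add is the count of patients not assessed in each arm.

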5.7.3. Vital Signs and Weights

Vital signs collected during the study include systolic and diastolic blood pressure, pulse, and temperature.

Continuous Analysis

For vital signs of blood pressure, pulse, and temperature as well as weight and BMI, the mean change from baseline to endpoint will be summarized.

The listing will be created

Categorical Analysis

The number and percentage of patients meeting criteria for abnormalities in vital signs and weight at any time during study will be summarized by treatment. [Table LAIH. 5.4](#) displays the criteria used to define abnormal changes in vital signs and weight. The last column of the table displays the patient populations defined by baseline categories; the abnormal categorical changes will be analyzed for each of those patient populations.

The criteria generally consist of 2 parts, an absolute threshold and a change from baseline amount. The absolute threshold in the criteria is based on 1) minimum post baseline when the direction is low; 2) maximum post baseline when the direction is high.

The change from baseline amount in the criteria is 1) decrease from baseline to minimum post baseline when the direction is low; 2) increase from baseline to maximum post baseline when the direction is high.

Table LAIH. 5.4 Criteria for Abnormal Categorical Changes in Vital Signs

Parameter	Direction	Criteria	Patients Population defined by Baseline Categories
Systolic BP (mm Hg) (sitting)	Low	≤ 90 and decrease ≥ 20	All patients; $>90; \leq 90$
	High	≥ 140 and increase ≥ 20	All patients; $<140, \geq 140$
	PCS High	≥ 180 and increase ≥ 20	All Patients; $<180, \geq 180$
Diastolic BP (mm Hg) (sitting)	Low	≤ 50 and decrease ≥ 10	All patients; $>50; \leq 50$
	High	≥ 90 and increase ≥ 10	All patients; $<90, \geq 90$
	PCS High	≥ 105 and increase ≥ 15	All Patients; $<105, \geq 105$
Pulse (bpm) (sitting)	Low	<50 and decrease ≥ 15	All patients; $\geq 50; <50$
	High	>100 and increase ≥ 15	All patients; $\leq 100; >100$
Weight (kg)	Low	(Loss) decrease $\geq 7\%$	All patients
	High	(Gain) increase $\geq 7\%$	All patients
Temperature (° C)	Low	$<35.6^{\circ} C$ and decrease $\geq 1.1^{\circ} C$	All patients; $\geq 35.6^{\circ} C$
	High	$\geq 38.3^{\circ} C$ and increase $\geq 1.1^{\circ} C$	All patients; $<38.3^{\circ} C$

Abbreviations: BP = blood pressure; bpm = beats per minute; C = degrees Celsius; kg = kilograms; mm Hg = millimeters of mercury; PCS= Potentially Clinically Significant.

In addition, number and percent of patients with postbaseline blood pressures and pulse in the following categories will be provided:

- Systolic BP: ≤ 90 mmHg, ≥ 140 mmHg, ≥ 160 mmHg
- Diastolic BP: ≤ 50 mmHg, ≥ 90 mmHg, ≥ 100 mmHg
- Pulse: ≤ 60 bpm, ≥ 100 bpm

5.7.4. Laboratory Tests

Continuous Analysis

For continuous lab values, observed value and the mean change from baseline to endpoint will be summarized. Create both standard and conventional units' outputs.

Categorical Analysis

The incidence rates of patients with high, or low laboratory values based on Covance reference ranges at any time post-baseline will be summarized.

Patients will be defined as having a low value if they have normal or high values at baseline, followed by a value below the lower reference limit at any post-baseline values. Patients with all normal or high values at baseline (no low values) will be included in the analysis of abnormal

low laboratory values. Patients will be defined as having a high value if they have normal or low values at baseline, followed by a value above the upper reference limit at any post-baseline values. Patients with all normal or low values at baseline (no high values) will be included in the analysis of abnormal high laboratory values.

For analytes simply classified as normal or abnormal, patients will be defined as having an abnormal value if they have normal values at baseline, followed by an abnormal value at any post-baseline visit. Patients with all normal values at baseline will be included in the analysis of abnormal laboratory values.

The incidence of patients with the following elevations in hepatic laboratory tests at any time post-baseline will also be summarized:

- The percentages of patients with an alanine aminotransferase (ALT) measurement greater than or equal to 3 times (3 \times), 5 times (5 \times), and 10 times (10 \times) the Covance upper limit of normal (ULN) during post-baseline period will be summarized for all patients with a post-baseline value.
- The percentages of patients with an aspartate aminotransferase (AST) measurement greater than or equal to 3 times (3 \times), 5 times (5 \times), and 10 times (10 \times) the Covance upper limit of normal (ULN) during post-baseline period will be summarized for all patients with a post-baseline value.
- The percentages of patients with an Alkaline phosphatase (ALP) greater than or equal to 2 times (2 \times) the Covance ULN during post-baseline period will be summarized for all patients with a post-baseline value.
- The percentages of patients with a total bilirubin (TBIL) measurement greater than or equal to 2 times (2 \times) ULN during post-baseline period will be summarized for all patients with a post-baseline value.

Hy's law is defined as the combination of elevation of $ALT \geq 3 \times ULN$ and $TBIL \geq 2 \times ULN$, in the absence of significant cholestasis ($ALP < 2 \times ULN$).

The analysis of elevation in ALT, AST, ALP, and TBIL will contain three subsets:

- Patients whose non-missing maximum baseline value is less than or equal to 1 \times ULN for ALT, AST, ALP, and TBIL.
- Patients whose non-missing maximum baseline value is greater than 1 \times ULN for ALT, AST, ALP, and TBIL, and at the same time less than or equal to 2 \times ULN for ALT and AST, 1.5 \times ULN for ALP and TBIL.
- Patients whose non-missing maximum baseline value is greater than 2 \times ULN for ALT and AST, 1.5 \times ULN for ALP and TBIL.

Note that patients with no corresponding postbaseline values will be excluded.

A listing of Subjects with abnormal Laboratory Results will be created.

A listing of Subjects with abnormal Hepatic Laboratory Results will be created.

